## Background

Currently there is no information about the most effective way to communicate information to patients following a dental check up. Important information to be communicated at the check-up is 1) the condition of the patients' mouth and 2) the likely risk of future disease and 3) what the patient needs to do in terms of self care. Although research has identified a link between effective clinical-patient communication and the adoption of health behaviours by patients (Wanyonyi et al, 2011), there is less research specifically on what *form* of information best facilitates this communication in order to form a 'therapeutic alliance'. We particularly do not know whether patients from different socio-economic backgrounds react differently to different forms of information, and how this influences the clinical-patient relationship and the patients' behaviour. This is something which is relevant not just to dental disease, but to a range of chronic conditions. Waldron et al (2011) for example, in a systematic review of effective strategies to communicate cardiovascular risk information to patients, highlight the lack of quality trials that compare different risk presentation formats.

Currently there is an emphasis on paper-based means of communicating risk and other information to patients. Reforms to the NHS dental contract are being piloted in 90 dental practices, with wider implementation anticipated in the next few years. The dental check-up forms a crucial part of this new model of care with all pilot practices patients with being given paper copies presenting their risk and oral health status as a traffic light (Red=High risk/need etc). This, however, is at odds with the government's ambition of a paperless NHS by 2018. Moreover, the Department of Health (2012) strategy 'The power of information', recognises the potential of technology 'to make the best use of evidence and support innovative approaches to behaviour change; and a relatively new technology currently exists which would allow the patients' oral health status and risk of disease to be presented as a photograph of their mouth with areas of the mouth at risk of disease highlighted using Quantitative light-fluorescence (QLF). QLF allows visualisation of tooth mineral loss at a stage before it is visible with the naked eye. It also highlights mature plaque which fluoresces red. Wireless technology allows transmission of these images to devices such as mobile phones. Literature reviews in the area conclude that visual displays (e.g. graphics) enhance people's understanding of risk, particularly holding attention when they are given in a vivid way (Rotham & Kiviniemi, 1999; Houts et al, 2006). Whilst all patients can benefit when pictures are used, people with low literacy skills are found to be especially likely to benefit (Houts et al, 2006). QLF presentation of oral disease risk is certainly vivid, but a Traffic Light presentation may be simpler - both are alternative forms of giving visual information.

What we do not know is whether using a newer technology to present information to patients at the dental check-up is something which is valued by patients, and merits the additional cost. Whilst technological developments in patient information systems are reported to be transformative in the nature of the interaction between patient and provider, there are

concerns about a possible age-based digital divide (Tang & Lansky, 2005), and that the use of e-health may widen ethnic and socio-economic health inequalities (Hsu et al, 2005). Our research then asks the question: 'What is the cost and value of purely verbal information on oral health and risk of disease, compared to information based on a Traffic Light presentation information or QLF images sent to mobile phones?'

# **Aims and Objectives**

**Aims:** To describe how patients value and respond to information on their oral health status and risk and to compare the value of three different methods for presenting information on patient's oral health and risk (verbal, paper-based traffic light rating, electronic QLF image)

## **Objectives:**

1. To describe what type of information patients' want, need and prefer when having a dental check-up and how they use this information.

2. To describe how patients' interact with three different forms of information

3. To investigate whether and how the clinician/patient relationship is influenced by patients having access to different types of information

4. To measure individuals' preferences, by using the economic preference based valuation methodology Willingness to Pay for each of the three different methods of giving information.

5. To identify differences in preference for different types of information by differing demographic, behavioural and psychographic groups.

6. To use variables from derived established models of the behavioural change process to predict the likelihood that different forms of communication will lead to behaviour change; and to measure any actual behaviour change and link these with differences in valuations

7. To conduct a cost-benefit framework analysis of the three different methods and to explore financial implications for NHS dentistry.

# **Research Plan**

# Overview

The work is divided into two phases: Phase 1 (months 1-12) which has three components which will run concurrently: a) a scoping literature review; b) a qualitative study involving interviews with patients and observation of patient care; and c) piloting of behaviour change and economic measures, and study procedures to be used in the second (experimental) phase. Phase 2 (months 13-24) involves an experimental study undertaken in four NHS dental practices involving patients being given different forms of information. In the final six months we will analyse and report Phase 2 quantitative findings and draw data streams together in final reporting.

## Consent, confidentiality and anonymity

All participants in the study will receive a written information sheet relating to their aspect of the study, and a written, signed consent obtained, before their involvement in the study. All participants will be free to decline any further involvement in the study at any point. Records identifying participants will use a system of ID numbers, with no names associated with data. Data related to the views of individual patients will not be divulged to members of the dental team caring for patients, and vice versa.

#### Phase 1

## a) Scoping literature review

We will undertake a scoping literature review (Levac et al, 2010) to map the existing literature and summarise findings concerned with how patients value and respond to health information given in different forms. This will be limited to a comparison of different forms of giving personalised feedback about health states or health risks (for example, but not limited to verbal, written, diagrammatic, photographic). Outcome variables of interest will include patients' preferences and economic valuations, objectively verified behavioural change, selfreported behavioural change and potential mediators of change including behavioural intentions and risk perceptions; as well as impacts on patient-carer communication and patient satisfaction. An analytic framework or thematic construction will be used to provide an overview of the breadth of the literature but not a synthesis. A numerical analysis of the extent and nature of studies using tables and charts will be presented. We will approach electronic searching iteratively, in the same way as recent approaches reviewing evidence in the public health sphere, where there is a deliberate use of a purposive sampling of the literature (Pawson et al, 2013; Baxter et al, 2010), rather than a focus on rigid inclusion criteria and exhaustive searching of all available articles. We will include in our review qualitative as well as quantitative studies.

## b) Ethnographic study on dental care

This qualitative study will help us to explore our first three objectives:

- To describe what type of information patients' want, need and prefer when having a dental check-up and how they use this information.
- To describe how patients' interact with three different forms of information
- To investigate whether and how the clinician/patient relationship is influenced by patients having access to different types of information

We will also seek to identify what patients' see as personally important negative outcomes from poor dental health in order to provide insights that will help us to develop the most appropriate measures of oral health behaviour to be used in the Phase 2 quantitative study.

Ethnography, as Laura Nader puts it (Nader, 2011), is research with rather than on people. In that sense, it reverses the polarity of much medical research: the patient is the expert in ethnographic research not the researcher or the health care practitioner. It involves spending time with people in order to find out from them how they do things, and getting a 'patient's eye view' of the matter. Medical anthropologists in particular have looked at all manner of

healthcare practices around the world from an ethnographic perspective for well over 100 years. In addition to medical anthropology, there is a great deal of work being done in the field of science and technology studies as with, for example, the studies of Anne-Marie Mol, perhaps most famously her The Body Multiple which looked at multiple sclerosis ethnographically (see http://www.dukeupress.edu/The-Body-Multiple/).

The purpose of ethnography is to provide in-depth accounts of people's views and behaviours as well as the significance of the inhabited space of the interaction. It is anticipated that the majority of ethnographic data collected will come from observing dental appointments, which can be considered the 'front-stage' of interaction (Goffman 1959). This recognises that dental staff and patients may behave differently in formal appointments than in other spaces and interactions. For example a dentist may accept a patients claim to be complying with treatment during an appointment (front-stage), but complain about lack of compliance to colleagues later on (back-stage). Observing either the front-stage or back-stage alone may produce a bias in only examining one part of the interaction. Ethnography provides the means to look at how risk is constructed and negotiated between dentist and patients within dental interactions. Cross-examining accounts with observations of dental professionals' everyday practices allows the discrepancies between what dentists and patients do and what they say to become apparent.

A researcher will observe dental visits in at least four NHS dental practices, investigating the type of information patients currently receive when having dental check-ups and whether they see information from the dentist in radically different ways to practitioners. The researcher will observe the dental visit itself, and take detailed field notes, but will not interfere or contribute to any discussions about care which take place. Field notes will be made during all observations, which will then be annotated immediately after the session to allow an authentic reconstruction of what was witnessed. The researcher may also interview the dentist or another member of the dental team after the clinical visit is finished, to explore some of the observations made.

Following this, patient interviews will take place away from the surgery itself to examine how patients interpret the information given during dental appointments and discuss the alternative forms of information giving the patient would want, need or prefer to receive. Discussion with these patients will involve their thoughts on paying for NHS care, or being exempt from charges, as well as any thoughts they have on changes in NHS dentistry involving a traffic light system of rating patients' risk and need (one of the messages they may receive from consultations, may be that without taking the appropriate action, they won't receive future treatments). This provides the background against which patients' readings of the information they receive will be set, and is highly relevant to studying how they orient to, interpret and act on that information. Where possible all interviews and some of the surgery conversations between the dental team members and the patients relating to information given at the check-up, will be audio-taped and transcribed for analysis.

We will purposively sample to include different adult groups and explore whether differences exist e.g. by age and socio-economic groups. We will explore barriers to healthy oral self-care, and the gains which are perceived to be possible through improvements in their oral health behaviour; looking to identify 'segments', particularly within the population of people at high/medium risk of oral disease, - groups with similar characteristics in terms of identity, lifestyle, opinions, beliefs and behaviours. We anticipate conducting in-depth one-to-one

interviews with patients, although the actual number itself will be guided by the qualitative research principle of data saturation – may be a few more or a few less depending on emergent findings (Spencer et al, 2003).

We plan to continue to observe within the study practices during Phase 2 to investigate how the clinician-patient relationship is influenced by the patients having access to the three different forms of information. In addition to Phase 1 observations within the study practices the researcher will also observe the traffic light system and the QLF technology in other dental settings not taking part in Phase 2. This will ensure there is no contamination with the study practices during Phase 1 but will allow the researcher to observe how the whole dental team react to the technology and traffic light system without the accompanying intervention of experimental study processes.

# Data analysis

Data sources from interviews, observations and ethnographic work will be integrated into a single analysis. Qualitative data analysis will adopt the principles of grounded theory which include a 'constant comparison' method, where interview texts are analysed line by line, provisional themes noted, and are subsequently compared with other transcripts in order to ensure consistency and to identify negative cases (Walker & Florence, 2006). Literature will be consulted as part of an iterative, inductive and interactional process of data collection, simultaneous analysis and emergent interpretation. Conceptual memos will be written alongside coding to document the development of codes, how codes are related to each other, and to existing theory in the area. Emerging perceptions from both the inductive and aggregate coding will be shared at 'data clinics' where project researchers meet to discuss and test emerging themes. Emerging concepts will be further probed and refined in interviews with the next participants to ensure validity of the data or to reject concepts which do not hold to further scrutiny. We will also involve members of the Research Advisory Group and some of the research participants to check the validity of our perceptions. A diary of thoughts and observations will be kept throughout the study and meetings with people involved in the analysis and interpretation of qualitative data, to provide opportunities to be reflexive about how researchers and the process of conducting research has influenced data collection and analysis. The software package NVIVO Version 10.0 will be used to aid indexing and retrieval, analysis and presentation of coding themes.

c) Preparation for Phase 2

# Overview of Phase 2

Phase 2 consists of an experimental design using randomisation at the patient level, of different forms of information (verbal information only, traffic light information QLF information) This will take place in four NHS dental practices (two in Salford, and two in Newcastle). We will collect patients' Willingness-To-Pay (WTP) for each of these types of information, as well as data on their perceived risk of dental disease and intended and actual behaviour change. Using clinical data (BPE scores measuring gingival health) and data on tooth mineral loss as well as plaque coverage measured from successive QLF photographs, we will also gather information on actual changes in oral health behaviours.

## Recruitment of practices

The four dental practices will be selected from a list supplied by NHS Area Teams in Salford and Newcastle where the practice involves more than one practitioner (single handed dental practices are unlikely to be able to offer the patient throughput necessary to achieve the target patient recruitment. Practices will be approached to invite them to be involved in the study on the basis of random selection, working down each list until two practices in each area are happy to participate in the study. We will recruit practices to the study which can confirm that their patient throughput of adult High/Medium risk patients is sufficiently high to ensure timely recruitment.

## Piloting of methods

In Phase 1, we will undertake a feasibility and pilot testing of methods of collecting the information which will form part of the Phase 2 dataset. Much of this could be gathered using a questionnaire format, although some may be extracted from patient information held on the clinical database, or by asking the patient directly in an interview. The most effective and efficient means of gathering the information will be piloted in Phase 1: Patient age, gender, Index of Multiple Deprivation (derived from postcode), patients' education level, household income level and socio-economic classification based on occupation, frequency of dental attendance, payment for dental care, dental experience of a variety of procedures, experience of dental pain and number of natural teeth remaining, risk perceptions (patient perceptions of the likelihood and potential severity of negative oral health outcomes; as well as willingness to pay, and intended, reported and objectively verified (with clinical outcome data) behaviour change.

University of Liverpool researchers (funded by HSDR) will train dental nurses in each of the four dental practices involved in the study to collect this formation as well as gather information on WTP. Piloting will involve taking members of the public and patients, including Patient and Public Involvement members of the project team through the WTP exercise and then discussing the process with them, to understand where improvements could be made.

Phase 1 preparation will also involve training dentists and dental team members to take QLF photographs and for clinical staff to interpret these and give information to patients. Dental team members will also receive training in Good Clinical Practice and study procedures such as: gathering consent for the study, undertaking randomisation procedures and completing study records such as recruitment logs etc. A checklist of the main preventive messages given by dentists to patients at the check-up will be produced for use in all three arms of the experimental study.

### Phase 2: Experimental study in four dental practices

The quantitative study will help us to address final four objectives:

- To measure individuals' preferences, by using the economic preference based valuation methodology WTP for the three different methods of giving information.
- To identify differences in preference for different types of information by differing demographic, behavioural and psychographic groups.

- To use variables from derived established models of the behavioural change process to predict the likelihood that different forms of communication will lead to behaviour change; and to measure any actual behaviour change and link these with differences in valuations.
- To conduct a cost-benefit framework analysis of the three different methods and to explore financial implications for NHS dentistry.

#### **Participants**

The study will involve 400 adult patients (aged 18 years or older), (100 in each of the four dental practices), who have been identified clinically as having high/medium oral health need/ risk of disease. We will use the nationally developed algorithm categorising patients as Red/Amber to define patients who are eligible for inclusion in the study. We will include patients will low literacy, but exclude patients who require an interpreter for dental care.

## Sample size calculation

As the primary outcome in this study is willingness to pay (WTP), this has been used to calculate the sample size. Differences in mean and median WTP values between the three forms of information are therefore the primary driver of sample size. Lancsar & Louviere (2008) highlight the complexities and problems of performing sample size calculations for stated preference surveys such as discrete choice experiments and contingent valuation studies (Lancsar & Louviere, 2008). In particular, the parameters that will be estimated by the CV survey (willingness to pay) must be known in advance in order to conduct a useful sample size calculation – information we do not have in advance of conducting this work. Previous studies however, using CV in health care settings have included samples ranging from less than 50 to over 1000 respondents. Recent CV work in dentistry has also used similar sizes (between 36 and 200 per group), albeit looking at treatments rather than provision of information (Rosvall et al., 2009). So, we believe that a sample size of 400 i.e. 133 in each group will be adequate in this case.

Whilst WTP is the primary outcome measure, and sample size calculation was done on this basis, we have however calculated the implications of this sample size for the detection of secondary (clinical) outcome effects. Thus we have also carried out a sample size calculation using the secondary outcome of plaque percent index (PPI), (measured using QLF). Published data on a group of 38 college students showed a mean PPI of 14.8, with a standard deviation of 7.7 (Aleksejuniene et al., 2006). As this is likely to be a more homogeneous population than in this study, we can use a more conservative estimate of s.d. of 10, to calculate that a sample size of 133 per group would allow us to detect a mean difference of 3.5 in PPI between groups, with 80% power, at the 0.05 significance level.

# **Randomisation**

After patients are recruited to the study, a trained nurse in each practice will the randomise patients to one of three study arms (Verbal information only (n=133); Traffic Light Information (n=133); QLF information (n=133). This will be done using a randomisation schedule for each practice, drawn up by the statistician ([name]); allocating patients using sequentially numbered envelopes. The envelope will be opened by the dentist at the check-up and procedure followed according to which study arm the patient has been allocated to.

## Procedures (see Flow diagram and Study Crib sheet)

# Visit 1 (V1):

Before their dental check-up, for patients recruited to the study a measure of the patients' literacy (REALM) will be administered by a dental nurse. The following data will then be gathered as self-reports: demographic (age, gender, income, education, employment status); psycho-graphic (previous experience of dental care, self-rated oral health, dental anxiety (MDAS); and oral health behaviours (diet, oral hygiene and smoking).

Information on patients' hypothetical incremental Willingness to Pay (WTP) for both the Traffic Light and QLF information systems (using Verbal information only as a base line for comparison), will be gathered. The systems will be explained hypothetically using written and visual information giving a generalised description of that type of information, but without reference to the patients' personal oral health status/risk. Following an outline of the 3 scenarios, patients will first be asked which of the forms of information is preferred including the current practice of Verbal information only (ranking) and then incremental WTP will be elicited for traffic light and QLF both compared to Verbal only (i.e. what extra would some be willing to pay (if at all) to receive either traffic light or QLF over verbal information only) in this face to face setting.

WTP will be elicited using a shuffled payment card method, where a range of values are shown to the patient one at a time in a random order (Smith, 2006). The participant then decides for each value whether they are willing to pay the amount, unwilling to pay it or unsure. This then leaves a range between the lowest value that the participant is unwilling to pay and the highest value that they are willing to pay. The patient will then be asked to name the value between (and including) these values that would be the maximum they would be willing to pay. The decision for each card therefore is similar to a dichotomous choice (as recommended by Arrow and Solow, 1993)), but the whole process finishes with an open ended question. This approach minimises some of the problems associated with using either one of these methods on their own, such as starting point and range bias and making the cognitive task too difficult. Where participants give a zero value, they will be asked to identify the reason for the zero valuation from a range of options presented verbally and on a card. This will allow zeros to be later classified as true zeros or protest responses.

Baseline QLF photographs will then be taken of all patients to measure plaque levels. The patients will then brush their teeth and a second QLF photograph taken to measure tooth mineralisation. At this stage there will be no disclosure of the photograph to patients.

Patients will then have their dental check-up appointment (which will include a BPE examination). The dentist will open the randomisation envelope and patients will then be given their own personal risk information according to the randomisation schedule: either 1) Verbal only information (Model 1) or 2) Verbal information supported by a printed copy of the patients' oral health and risk of disease displayed as a traffic light (Red, Amber or Green), (Model 2) or 3) Verbal information supported by the QLF photographs taken earlier.

In the QLF arm the dentist will discuss the images with the patient in an electronic form on a Tablet PC. These patients will be offered an e mailed electronic image and/or a printed copy of the most meaningful image (either plaque or mineral loss) in a credit card size. A record will be made if an electronic image is sent. In the Traffic Light arm patients will be given a

credit-card sized information showing their risk level according to colour on the card. In the Verbal only arm patients will receive a plain card with a checklist where the message given by the dentist is written. The reverse of the credit-card sized information from the QLF arm and the Traffic Light arms will have the same checklist (Figure 1):

Figure 1: Checklist of possible preventive messages given to patients

- Stopping or quitting smoking
- Following your dental treatment plan

Following the check-up the dentist or nurse will record as data variables:

- The number of natural teeth present
- Whether the patient is exempt or not from NHS charges
- Any messages given as checked against the Figure 1 list
- The Red, Amber or Green risk rating assigned to patients in the Traffic Light arm

Following the dental appointment, all patients will be given the opportunity to revise their WTP for the information form experienced (therefore this will not be relevant to those in Model 1 who receive only verbal information and they will not undertake this part of the study). For this re-valuation, patients will be reminded of their initial valuation and then asked in a single open-ended question format if they wish to change the value and what amount they would change to.

Self-report data will then be collected at this point on:

- Intention to behave according to the behaviours listed in Figure 1 before the next appointment
- Behaviour change variables as outlined by the Extended Parallel Process Model (EPPM) (Severity of Threat, Susceptibility of Threat, Self-Efficacy and Response Efficacy). The 'threat' here will be the threat of poor oral health and its consequences identified from Phase 1 (for detail see Measures: 5b Risk (threat) perception). An additional set of items will be added to reflect affect concerned with negative oral health outcomes i.e. '*How would you feel if...*' (in addition to the cognition set reflected in EPPM domains).
- Patient-Clinician communication (Communication Assessment Tool, CAT).

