## Phase 2 Analysis

# WTP

We will compare hypothetical Willingness to Pay for each of the information systems across the whole sample (primary outcome) across the 3 arms. We will also compare hypothetical WTP with WTP for a good that has been "consumed" by comparing WTP before and after receiving the information. WTP data will be analysed both descriptively, comparatively and econometrically. Descriptive data analysis will consist of WTP value means with standard deviations along with medians and quartiles for each information system. The WTP values for each system will be compared using appropriate comparative tests (e.g. most likely to be Mann Whitney U tests given the likely distribution).

In order to understand fully how the dental and demographic factors influenced values (WTP), econometric regression analyses will be carried out. A regression model of individual co-variates on WTP will be specified. The regression method will be dependent on the data but is likely to be either OLS or Tobit regression analyses. Tobit models have been recommended for analysis of WTP data because of the censoring of the data at zero (Halstead et al., 1991). The Ramsey RESET test will be used to test for model specification. Individual Tobit models will be constructed for each information system.

Finally, hypothetical WTP data for each information form will be compared to WTP following experience again using the most appropriate comparative tests.

Probable hypothesis tests to be used to compare WTP for different arms and also at different time points and econometric analysis plans to analyse factors that influence WTP. The Ramsey RESET test (Ramsey, 1969) will be used to test for model misspecification. The RESET test tests for omitted variables, incorrect functional form and correlation between independent variables and the error term. Sensitivity analysis using alternative regression analysis (e.g. tobit, OLS Interval regression analysis) will be performed to test whether the results are sensitive to model specification.

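### The protocol neither states nor counterbalances the order in which each patient values Traffic Light and QLF; if one order is used, an order effect cannot be told apart from format in that part of the primary outcome

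*Protocol*

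**What the plan says.** The protocol's WTP analysis section sets the primary outcome: "We will compare hypothetical Willingness to Pay for each of the information systems across the whole sample (primary outcome) across the 3 arms".

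Under Procedures, Visit 1, these values are collected face to face before the check-up. Each patient gives "hypothetical incremental Willingness to Pay (WTP) for both the Traffic Light and QLF information systems", with Verbal as the baseline. The sequence begins as follows: "Following an outline of the 3 scenarios, patients will first be asked which of the forms of information is preferred". The two valuations come next: "incremental WTP will be elicited for traffic light and QLF both compared to Verbal only".

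Within each valuation the card amounts are shuffled: "a range of values are shown to the patient one at a time in a random order". The protocol says that its elicitation method limits starting-point and range bias.

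Allocation comes later, at the check-up: "The dentist will open the randomisation envelope and patients will then be given their own personal risk information according to the randomisation schedule".

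Neither the procedures nor the list of measures says which format is described or valued first, or that the order is recorded. The WTP analysis section mentions no order term. The Procedures heading refers to a flow diagram and a study crib sheet, which are not available here.

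**The concern.** The Traffic Light versus QLF contrast is the difference between two answers that the same person gives a short time apart. The first answer can act as an anchor for the second, and the format described last may be fresher in mind. The protocol guards against this kind of bias within one valuation by shuffling the cards. It has no matching safeguard between the two valuations.

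Randomising patients to arms does not help, because the hypothetical values are complete before the envelope is opened. Nor can the analysis plan repair the gap afterwards. If order never varied, there is nothing to adjust with. If it varied by nurse or practice but was not recorded, it cannot be adjusted for either.

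Two results depend on this contrast: the comparison of formats in the primary outcome, and the incremental net benefit in the cost-benefit framework analysis, which is mean WTP minus mean cost. A shift in one format's mean WTP passes pound for pound into its net benefit. The re-valuation after the check-up reminds patients of their first figure, so a distorted value may persist there too.

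**Working it through.** **The plan's own figures.** The Sample size calculation section gives no WTP effect and no WTP SD, so there is no WTP calculation to reproduce. The only power statement concerns plaque (133 per group, difference 3.5, SD 10, 80% power at 0.05). It checks: 3.5 / (10 × √(2/133)) = 2.854; 2.854 − 1.960 = 0.894; power 0.81. It has no bearing on order.

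**Inputs.** n = 400 (Participants section). Two-sided 0.05 is assumed. Let c be the order effect, in units of the SD of the paired difference (QLF minus Traffic Light), and let there be no true format difference. The documents give no value for c, so a range is shown. Let p be the share of patients who value Traffic Light first.

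**Bias.** Bias = c × (2p − 1).
- One order for everyone (p = 1): bias = c.
- Mixed, uncontrolled order, with c = 0.10: p = 0.60 gives 0.10 × 0.20 = 0.02; p = 0.75 gives 0.10 × 0.50 = 0.05.
- Randomised 1:1 (p = 0.5): expected bias = 0.

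**False-positive rate, paired test, one order for all.** The test statistic is centred at c√400 = 20c. The rate is P(|Z + 20c| > 1.96).

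| c | 20c | Rate |
|---|---|---|
| 0.05 | 1 | 0.170 |
| 0.10 | 2 | 0.516 |
| 0.15 | 3 | 0.851 |
| 0.20 | 4 | 0.979 |

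For scale, 400 pairs detect (1.960 + 0.842)/√400 = 0.14 SD with 80% power. An order effect near that size would look like a real format effect.

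**Same shifts under an unpaired test.** The WTP analysis section expects Mann Whitney U tests. Take a normal approximation with equal SDs and correlation ρ between a patient's two values (also an assumption). Ignoring the pairing makes the rate P(|Z + 20c| > 1.96/√(1 − ρ)).

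| ρ | Threshold | c = 0.05 | c = 0.10 | c = 0.20 |
|---|---|---|---|---|
| 0.3 | 2.34 | 9% | 37% | 95% |
| 0.6 | 3.10 | 1.8% | 14% | 82% |
| 0.8 | 4.38 | 0% | 1% | 35% |

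The rate therefore depends on the test as well as on c. The bias in the mean difference does not depend on the test: under one order it stays at c.

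**Cost of counterbalancing.** With half the patients shifted by +c and half by −c, the SD of the difference grows by √(1 + c²): 1.001 at c = 0.05 and 1.02 at c = 0.20. An order factor in the model takes out this extra spread as well.

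**The case against.** The strongest reply is that the protocol is silent and does not fix an order. Naming Traffic Light before QLF is a list, not a sequence. The interview order could be set in the crib sheet, and the WTP exercise is to be piloted and improved in Phase 1. This stands. A reader might infer that a fixed order is used and that order is therefore wholly confounded with format. The documents do not support that: it follows only if every patient has the same order, and with mixed orders the confounding is partial or nil.

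Second, patients hear all three scenarios and rank them before naming any amount, and each format is valued against Verbal rather than against the other. This plausibly reduces anchoring, and the ranking gives a non-monetary check on the direction of preference. It does not remove the problem: the outline has an unstated order too, and the two valuations still follow one another.

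Third, the percentages are not evidence about this trial. They rest on an assumed effect size and on a paired test that the protocol does not name. This also stands, and they serve only as illustration.

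Fourth, a reader might infer that the whole primary outcome is compromised. That goes too far. Each increment over Verbal is itself a comparison, and the increment valued first is not anchored by an earlier valuation. The point is limited to Traffic Light versus QLF.

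What survives is that order is a feature of data collection, and the protocol describes the elicitation step by step without controlling or recording it.

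**Conclusion.** The point holds as a conditional design gap. The protocol randomises card amounts but neither states nor counterbalances the order of the two formats. If a single order is used, the bias in the Traffic Light versus QLF difference equals the whole order effect, and no later analysis can separate the two. If order varies without control, the bias is a fraction of that effect.

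The size is unknown, because the documents give neither an order effect nor a WTP SD. Under the stated assumptions (no true format difference, paired test, one order for all 400), effects of 0.05 to 0.20 SD give false-positive rates of 17% to 98%. Under an unpaired test the rates are lower over the correlations shown. The case for acting does not rest on these figures: balancing the order makes the expected bias zero at almost no loss of precision. This is a cheap improvement, not a flaw that invalidates the trial.

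**What to change.** In Procedures, Visit 1, state that the format described and valued first (Traffic Light or QLF) is randomised 1:1 within practice, and that the order is recorded for each patient. In the WTP analysis section, include order as a factor in the comparison and report the format difference averaged over both orders.

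Use a sequence separate from and independent of the arm allocation. The per-practice arm schedule is held in envelopes that the dentist opens at the check-up, after WTP has been elicited. Drawing the order from it would mean consulting it early, which threatens concealment, or tying order to arm.

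The cost is two versions of the script, a second short sequence per practice, one data field and brief nurse training. No extra patients are needed. If the crib sheet already randomises and records the order, it is enough to say so in the protocol and add the order term to the analysis.
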